The primary adverse event of concern in this study would be thromboembolic events. DSMB (anesthesiologist, hematologist, and statistician) will meet quarterly, and review all data from each study arm. Thromboembolic complications will be reviewed and clinical judgment will used to determine necessity of study termination. No formal stopping rules are feasible given the study size and low incidence of TEE.

Early termination of the study will ensue if adverse events in either study arm exceed acceptable level.

D. Randomization and Blinding

Upon consent for study participation enrolled patients will be randomized via computer-generated blocks and with stratification according to the surgical procedure to either receive PCC or FFP during cardiac surgery should they develop excessive microvascular bleeding in the

surgical field as determined by the surgical team in addition to a PT >16.6 sec/ INR >1.6 sec after cardiopulmonary bypass. The randomization assignments will be concealed in opaque envelopes and disclosed to the anesthesiologist caring for the patient. The surgical and intensive care personnel will not be blinded to the treatment arm, as transparency of transfusion product is necessary to prevent overdosage of PCC and potential thrombotic complications.

E. Interventions

Patients will be consented and enrolled in the study until 50 patients have received treatment in each arm of the study. Patients will be anticoagulated according to institutional practice with heparin 400 units/kg with goal ACT >400 prior to initiation of cardiopulmonary bypass. After cardiopulmonary bypass, patients will receive protamine at dose 0.01 mg/unit of heparin given with target ACT within 10% of baseline value. After protamine administration the ACT, CBC, PT/ INR, and fibrinogen, will be collected via preexisting arterial access. If ACT >10% baseline additional protamine will be given at the anesthesiologists discretion. Evaluation and determination of excessive microvascular bleeding in the surgical field will occur 10 minutes after return of ACT to within 10% of baseline. Patients with clinical evidence of excessive microvascular bleeding in the surgical field as determined by the surgical team, along with a PT >16.6 sec/ INR >1.6 sec will receive randomized treatment with either PCC or FFP.

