6. Postoperative variables:
- a. Allogenic blood product transfusion
 - b. Mediastinal and chest tube output for 24 hours after chest closure
 - c. **Serious Adverse Events** occurring within 30 days of operation:
 - i. Thromboembolic events (new DVT or arterial thrombosis diagnosed by Doppler ultrasound, cerebrovascular accident or transient ischemic attack, new myocardial infarction, end organ ischemia secondary to thromboembolic phenomenon, all-cause mortality)
 - 1. The concern for thromboembolic complications is certainly present, and will be monitored closely as an adverse event in both treatment arms. The presence of clinically significant thromboembolic complications will be diagnosed as per current clinical practice in this patient population. It is assumed that clinical symptomatology or suspicion to such diagnoses will trigger diagnostic testing when deemed appropriate, and any confirmed diagnoses of thromboembolic complications will be noted. No specific screening tests will occur in patients enrolled for this study.
 - ii. Renal failure necessitating unplanned initiation of dialysis or hemofiltration
 - iii. Acute Respiratory Distress Syndrome (ARDS) by Berlin definition¹⁷
 - iv. Direct transfusion related complications/reactions
 - 1. TRALI (Transfusion related acute lung injury) by standard definition¹⁶
 - 2. ABO/Non-ABO hemolytic reaction
 - 3. Anaphylactic or Allergic reaction
 - d. Length of stay (ICU and total hospital stay)

H. Outcomes

All suspected outcome events will be evaluated in a standardized way by an adjudication panel that will be unaware of the patients' assignments.

In the study, outcome measures for efficacy will be total allogenic blood products transfused and 24 hour postoperative blood loss. Outcome measure for safety will be rate of serious adverse events.

Length of stay in the ICU and hospital will also be recorded in both groups.

I. Follow-Up

A telephonic assessment will be made by a study nurse at 30 days + 7 days. A standardized phone survey will be used to obtain information for assessing events of interest (Attached below).

J. Statistics/Power Analysis

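### The thromboembolic part of the safety comparison is open to unequal detection between arms, and the plan includes no check of who was tested

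*Combined protocol and SAP*

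**What the plan says.** Four parts of the combined protocol and SAP bear on this.

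- **How events are found (3.G, item 6.c.i).** Diagnosis follows usual practice: "It is assumed that clinical symptomatology or suspicion to such diagnoses will trigger diagnostic testing when deemed appropriate". The item adds "No specific screening tests will occur in patients enrolled for this study" and says that "any confirmed diagnoses of thromboembolic complications will be noted". DVT and arterial thrombosis count when shown by Doppler. All-cause mortality is listed inside the same thromboembolic definition. The printed data list has no entry for tests ordered or for negative results.
- **Who knows the arm (3.D).** "The surgical and intensive care personnel will not be blinded to the treatment arm". The stated reason is that "transparency of transfusion product is necessary to prevent overdosage of PCC and potential thrombotic complications". The assignment is also disclosed to the anesthesiologist.
- **Safeguards (3.H, 3.I and the telephone script).** "All suspected outcome events will be evaluated in a standardized way by an adjudication panel that will be unaware" of the assignment. "A telephonic assessment will be made by a study nurse at 30 days + 7 days", using a standard script that asks about doctor visits, changes in health, clots, heart attack, stroke and dialysis.
- **How the result is used (3.C, 3.H, 3.J and 3.P).** Section 3.C names thromboembolism as the leading adverse event of concern. It leaves termination to the DSMB's clinical judgment, without formal stopping rules. The safety outcome is the rate of all serious adverse events. Section 3.J classes it as exploratory. Section 3.P equates safety with a similar rate in the two arms and gives no margin.

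**The concern.** The staff who would ordinarily order a Doppler or a scan know which product the patient received. The protocol itself links that knowledge to worry about thrombosis with PCC. If the threshold for testing differs by arm, the detected rates will differ even when the true rates do not. The opposite can also happen, so that a real difference is hidden.

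A blinded panel works downstream of this. It can reject a false positive, but it cannot find an event that was never suspected.

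Two uses of the data are exposed. One is the DSMB's judgment, where few events are expected and one or two extra detections could matter. The other is the closing statement that the rates are similar. Because the plan does not tabulate testing, a reader of either result could not tell who clotted from who was tested.

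**Working it through.** **Plan's own figure.** The documents give no calculation on this point and no thromboembolic event rate, only that incidence is low. The one design calculation is the power for chest tube drainage: 0.65 SD, 50 per group, above 85%. With two-sided alpha 0.05 (assumed), it reproduces at 90.1% by the normal approximation and 86.6% by the Noether formula. It concerns efficacy and does not bear on this point.

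**Step 1: which events depend on discretionary testing.**

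| Component or route | Depends on a clinician's choice to test? |
|---|---|
| DVT, arterial thrombosis | Yes; counted when shown by Doppler |
| Stroke with clinical deficit | Less so; the deficit itself prompts attention |
| All-cause mortality | No |
| Telephone survey | Independent of ward staff, but mainly returns events already symptomatic or diagnosed; a reported symptom with no Doppler does not meet the DVT definition |
| Blinded panel | Depends on an event having been suspected |

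The exposure is therefore partial and concentrated in the first row.

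**Step 2: illustrative size with equal true rates.** Inputs: n = 50 treated per arm (3.C, 3.E, 3.J, 3.P; the Specific Aims say 100, which is a separate inconsistency). Assumed, not in the documents: detection of 60% under FFP and 90% under PCC, and true rates of 5% to 20%.

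Observed rate = true rate × detection probability. Observed risk ratio = 0.9/0.6 = 1.50, or 0.6/0.9 = 0.67 if reversed. The 95% half-width is 1.96 × √[a(1−a)/50 + b(1−b)/50], where a and b are the observed rates.

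| True rate, both arms | Observed FFP v PCC | Expected events per 50 | False difference (points) | 95% half-width (points) |
|---|---|---|---|---|
| 5% | 3.0% v 4.5% | 1.5 v 2.25 | 1.5 | 7.4 |
| 10% | 6.0% v 9.0% | 3.0 v 4.5 | 3.0 | 10.3 |
| 15% | 9.0% v 13.5% | 4.5 v 6.75 | 4.5 | 12.4 |
| 20% | 12.0% v 18.0% | 6.0 v 9.0 | 6.0 | 13.9 |

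The false difference runs from one fifth (1.5/7.4 = 0.20) to under half (6.0/13.9 = 0.43) of the half-width.

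**Step 3: this is an upper illustration.** It applies unequal detection to every event. If only a fraction f of events depends on testing and the rest are always found, the ratio is (1 − f + 0.9f)/(1 − f + 0.6f) = (1 − 0.1f)/(1 − 0.4f). This rises from 1 at f = 0 to 1.5 at f = 1.

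**Step 4: masking and exaggeration.** Suppose the true rates are 10% under FFP and 20% under PCC.

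- Detection 90% FFP, 60% PCC: 0.10 × 0.9 = 9% v 0.20 × 0.6 = 12%, ratio 1.33.
- Detection 60% FFP, 90% PCC: 6% v 18%, ratio 3.0.

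Even with perfect detection, Fisher's exact test has only about 20% power for 10% v 20% at 50 per arm, and about 6% for 5% v 10%.

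**The case against.** The case against has real force.

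- **There are other routes to an event.** A reader might infer that events surface only when unblinded clinicians test. The documents do not support that: the telephone survey is the same for both arms, and death needs no test. What remains is that the survey rarely uncovers an untested event, and the text does not say whether the nurse is blinded.
- **No bias is shown.** A reader might also infer that the comparison is biased, probably against PCC. Nothing in the documents shows that testing will differ. The stated reason for unblinding chiefly concerns product dosing, so its effect on later surveillance is inference. The direction is open.
- **Testing could be checked later.** In-hospital orders should be in the medical record, so it would be wrong to say that unequal testing can never be examined. The gap is that no such check is planned.
- **Only part of the safety outcome is affected.** It also covers dialysis, ARDS and transfusion reactions, and it is exploratory. The affected part is nevertheless the one the protocol ranks first.
- **The panel may already see some negatives.** Suspected events could be read to include patients who tested negative. The text does not settle this, and the data list makes no provision for such reports.
- **Sampling error is larger.** This is true across the range shown. But detection bias adds to sampling error, and a confidence interval does not display it.

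**Conclusion.** The point holds as a limited one. The thromboembolic component is open to differential detection in either direction, and the plan neither measures that nor mentions it among its limitations. Its size cannot be derived from the documents. The risk ratio of 1.5 (or 0.67) rests entirely on assumed detection of 90% v 60% applied to all events, and the resulting shift is smaller than sampling error at 50 per arm. Imprecision and the lack of a margin for similarity limit the safety conclusion at least as much.

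The documents do not support concluding that bias is present, that the whole safety comparison is compromised, or that screening or staff blinding must change. They do support a cheap addition that lets a reader judge whether a difference, or a similar rate, could reflect who was tested.

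**What to change.** - **3.G item 6.c.i:** abstract every diagnostic test done for suspected thromboembolism up to day 30, with type, date, indication and result, negatives included.
- **3.H:** send all of these reports, plus positive telephone-survey answers, to the existing blinded panel with the arm removed.
- **3.J:** report by arm the proportion of patients tested and the yield per test. Report all-cause mortality separately from thromboembolic events. Add a descriptive sensitivity summary limited to the events least dependent on discretionary testing: death and stroke with clinical deficit. Ischemia defined by a need for intervention should not be in that summary, because the decision to intervene rests with the same unblinded staff.
- **3.L and 3.P:** state the limitation beside any conclusion that the rates are similar.

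The cost is modest abstraction time for about 100 treated patients and one more table. No screening, change of care or change to unblinding is involved. The check has limits: tests done elsewhere after discharge may be missed, the sensitivity summary will rest on very few events, and unequal testing will be revealed but not removed.

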Post-cardiopulmonary bypass coagulopathy and bleeding represents one of the largest areas of blood product transfusion in surgical practices today. Abnormal bleeding necessitating blood product transfusion occurs in about 11% of cardiac surgical patients.¹ Bleeding after cardiopulmonary bypass is multifactorial and related largely to blood exposure to bypass circuit components. Consequential coagulation aberrations include thrombocytopenia, platelet dysfunction, clotting factor consumption and dilution, hyper-fibrinolysis, and hypofibrinogenemia.³ Surgical field and bypass circuit blood which is processed through cell salvage processing and then transfused to the patient is devoid of remaining coagulation factors.^{4,5} Standardized transfusion algorithms for patients with post-cardiopulmonary bypass bleeding are not utilized across all healthcare institutions; however, algorithm based transfusion is standard practice at our institution.¹ Currently, patients with factor mediated coagulopathy and bleeding after cardiopulmonary bypass at our institution receive transfusion of fresh frozen plasma.¹ Factor concentrations within FFP are variable, and large volumes of transfused product are often necessary to correct factor deficiencies. In addition FFP transfusion carries the risk of transfusion related lung injury, transfusion related circulatory overload, infectious and allergic complications among others.⁶

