Prothrombin complex concentrate use in hemophiliac patients dates back several decades, and has recently become the treatment of choice for management of bleeding in patients taking vitamin K antagonists (warfarin).⁷⁻⁹ Current formulations of inactivated PCC available in the United States include Bebulin (Baxter) which contains factors 2, 9, 10, and Kcentra (CSL Behring) which contains factors 2, 7, 9, 10. PCC administration in the perioperative setting including post-cardiopulmonary bypass coagulopathy and bleeding is common in European countries. Studies evaluating the efficacy of PCC's in this patient population have demonstrated faster normalization of INR, lower blood loss, and lower transfusion requirements.^{2,10,11} Historically, PCC use in the perioperative setting has been limited due to fear of thrombotic complications. Newer formulations of PCC's include a variety of anti-coagulants such as heparin, protein C & S, and anti-thrombin 3. Such additives are felt to reduce thrombotic risk when compared to PCC formulations void of these additives.¹² Thromboembolic events remain a concern when using any procoagulant including PCC's, especially formulations with activated factors such as FEIBA (Baxter), which contains activated factor 7. Inactivated PCC use has not been directly linked to significantly higher rates of adverse outcomes or thrombotic complications when compared to conventional therapies in surgical patients.^{2,10,13} Large prospective randomized trials comparing PCC and FFP in cardiac surgical patients to assess clinical outcomes and safety have not been performed. Distinct advantages to PCC administration compared with FFP include higher factor concentration despite significantly less infusate volume, ambient storage with rapid reconstitution, unnecessary blood group compatibility, lower risk of transfusion related complications such as acute lung injury and infection, along with potential cost savings.¹⁴ Current transfusion practices in European countries involve use of inactivated PCC in lieu of FFP.

The significance of this study is related to the potential for reduction in allogenic transfusion requirements and hence associated transfusion related complications. Transfusion reduction would also lead to institutional cost savings which in busy cardiac surgical practices could be

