PCC (Kcentra) Dosage: Patients randomized to the PCC arm with evidence of microvascular bleeding and PT >16.6 sec/ INR >1.6 sec will have Kcentra 15 units/kg prepared from pharmacy.

Patients who have received **PCC** and continue to demonstrate microvascular bleeding 10 minutes after the full PCC dose has been administered will undergo repeat laboratory evaluation of PT/INR +/- CBC, and fibrinogen depending on previous lab results and product administration other than PCC. Therapy will ensue following our institutions current transfusion algorithm. Patients who received full dose PCC and continue to have microvascular bleeding in addition to a PT >16.6 sec/ INR >1.6 sec will receive FFP at a dose of 10-15 mL/kg rounded up to the nearest unit.

FFP dosage: Patients randomized to the FFP arm will continue with standard therapy per our institutional algorithm at a dose of 10-15 mL/kg rounded up to the nearest unit. Patients who have received **FFP** by randomization per the above dosage protocol and continue to demonstrate microvascular bleeding 10 minutes after product administration will undergo repeat laboratory evaluation of PT/INR +/- CBC, APTT, and fibrinogen depending on previous lab results and product administration other than FFP. Therapy will ensue following our institutions current transfusion algorithm. Patients who receive FFP per randomization and continue to have microvascular bleeding 10 minutes after product administration in addition to a PT >16.6 sec/ INR >1.6 sec, or aPTT > 57 sec will receive additional FFP.

Transfusion of coagulation products other than PCC or FFP (e.g. platelets and cryoprecipitate) will be determined by laboratory abnormalities requiring treatment within our institutions current algorithm in the presence of excessive microvascular bleeding.

Resolution of microvascular bleeding within the surgical field as determined by the surgical team is the endpoint for necessitation of transfusion, not normalization of coagulation testing.

Examples of this are as follows:

1. A patient with an INR of 1.9 and evidence of microvascular bleeding who receives either PCC or FFP, for which the microvascular bleeding resolves but the INR remains elevated at 1.7 would not receive additional transfusion.

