Power Analysis was determined from a study by Arnekian et al that retrospectively presented a reduction in blood loss in patients receiving PCC over those receiving FFP.² In that study, the distribution of 24-hr chest tube drainage was highly skewed, but the observed difference between the two groups was at least 0.65 standard deviation units. Using a non-parametric test, a sample-size of **N=50 per group should provide statistical power of >85% to detect a difference of this magnitude. Therefore we suggest a sample-size of at least 50 per group.** In the paper, they also found a dramatic difference in ICU red cell transfusions. If the true difference is as large as they observed a sample-size of N=50 per group would also provide adequate statistical power for this endpoint.²

Primary endpoints in this study will be units of allogenic blood product administration, and 24 hour postoperative blood loss. Exploratory endpoints will include rate of serious adverse outcomes.

Baseline patient characteristics, including demographics, comorbidities, preoperative laboratory values, and cardiovascular variables will be reported and compared across treatment groups. Categorical variables will be reported as counts and percentages, and compared across groups using chi-square or Fisher's exact tests. Continuous variables will be reported as median and interquartile ranges, and compared across groups using Wilcoxon rank sum tests.

K. Feasibility and Time Frame

This study with the combined collaboration of divisions of anesthesiology and cardiovascular surgery is quite feasible. Approximately 2200-2500 cardiopulmonary bypass procedures are done annually at St. Mary's Hospital. Making the conservative estimate that 50% will consent 1000 patients should be consented within 1 year. Given that approximately 11% of patients

receive transfusion; this would result in approximately 100-110 patients to be treated within 12 months. We expect to get IRB approval within the next one month. The study and data collection will take about 1 year with approximately two months for data analysis.

L. Strengths and Limitations

Strengths: This will be the first prospective randomized controlled trial in the United States directly assessing the effect of PCC compared to FFP in the setting of postcardiac surgery coagulopathy and bleeding in patients undergoing elective cardiac surgery.

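### The serious adverse event list omits circulatory overload, a harm the protocol itself attributes to FFP, so overload enters the safety comparison only if it also meets another listed event

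*Combined protocol and SAP*

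**What the plan says.** Section 1 (Background and Significance) states that "FFP transfusion carries the risk of transfusion related lung injury, transfusion related circulatory overload, infectious and allergic complications among others", and that "large volumes of transfused product are often necessary to correct factor deficiencies". Among the advantages of PCC it gives "higher factor concentration despite significantly less infusate volume" and "lower risk of transfusion related complications such as acute lung injury and infection".

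Section 3.E (Interventions) has the FFP arm continue with "standard therapy per our institutional algorithm at a dose of 10-15 mL/kg rounded up to the nearest unit". PCC patients who keep bleeding and still meet the laboratory threshold also receive FFP at that dose.

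Section 3.G (Data Collection) has an item called "Direct transfusion related complications/reactions" in two places: 5.i among the intraoperative variables, and 6.c.iv among serious adverse events within 30 days. Both contain the same three entries: TRALI, hemolytic reaction, and anaphylactic or allergic reaction. The rest of item 6.c covers thromboembolic events (with all-cause mortality placed under them), renal failure needing unplanned dialysis or hemofiltration, and ARDS.

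Section 3.H (Outcomes) states: "Outcome measure for safety will be rate of serious adverse events". It also sends suspected outcome events to a panel unaware of assignment. Section 3.J (Statistics/Power Analysis) gives the safety rate a lower rank: "Exploratory endpoints will include rate of serious adverse outcomes". Section 3.P (Human Subjects) nevertheless defines safety as a similar serious event rate in the two arms, without a margin.

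**The concern.** The protocol names a comparator harm in its rationale and then gives it no place among the events it collects. Followed as written, a patient with circulatory overload and none of the listed events is event-free in the safety rate, in either arm.

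The arm given plasma by weight-based volume is the one in which the protocol's own rationale points to overload. Uncounted cases would therefore more likely fall in the FFP arm, and the comparison would flatter FFP to some degree. A judgement that rates are similar, or that PCC is worse, would then rest on an incomplete count of serious harm. The trial would also have no data on a harm related to the volume advantage it claims for PCC.

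**Working it through.** **1. The plan's own figure.** The plan gives no figure for safety events. Its only computed figure is power above 85% for a 0.65 SD difference in blood loss with 50 per group. Assuming a two-sided 5% test and no dropout, power = Φ(0.65 × √(50 × ARE / 2) − 1.96), where ARE is the efficiency of the rank sum test relative to the t-test.
- ARE 1.0: Φ(3.25 − 1.96) = 90.1%
- ARE 0.955: 88.8%
- ARE 0.864 (worst case): 85.6%

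The figure reproduces. It has no bearing on safety.

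**2. Is overload captured anywhere else?**
- *Items 5.i and 6.c.iv:* overload is absent, and there is no category for other reactions.
- *Rest of item 6.c:* a case counts only if it also becomes ARDS, dialysis or hemofiltration, death or another listed event.
- *Other Section 3.G variables:* products transfused, chest tube output and length of stay are recorded. Fluid balance, oxygenation, pulmonary edema and ventilation time are not, so overload could not be reconstructed later from the listed data.
- *Telephone script:* questions 1 and 2 are open but concern the time since discharge. Question 3 names clots, heart attack, stroke and kidney damage needing dialysis. Overload during the hospital stay is not elicited.
- *Adjudication:* the panel receives suspected outcome events, and overload is not one.

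**3. Volume involved.** At 10-15 mL/kg and an assumed 80 kg, one FFP dose is 800-1200 mL. At an assumed 120 kg it is 1200-1800 mL. Both are before rounding up to whole units and before any repeat dose. The documents give no PCC volume in mL.

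**4. Possible number of uncounted events.** Let F and P be the overload rates in the FFP and PCC arms, and c the share of cases that also meet a listed event, taken as equal in both arms. The error in the between-arm difference is 50 × (F − P) × (1 − c) events. The documents give none of these values. With P = 0 and c = 0, F = 2%, 6% or 10% gives 1, 3 or 5 events. These are upper values for those F: P is unlikely to be zero, because PCC patients can receive rescue FFP and both arms can receive other products and fluids. With equal rates the error is zero.

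**5. What adding the item could show.** All rates are assumed. The uncounted difference takes c = 0. Power is two-sided 5% with 50 per arm, and the last column uses the chi-square approximation.

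| FFP / PCC rate | Uncounted difference | Power, Fisher exact | Power, chi-square | N per arm for 80% |
|---|---|---|---|---|
| 5% / 1% | 2.5 − 0.5 = 2 | 2% | 21% | 285 |
| 10% / 2% | 5 − 1 = 4 | 19% | 39% | 138 |
| 15% / 2% | 7.5 − 1 = 6.5 | 51% | 65% | 72 |
| 20% / 5% | 10 − 2.5 = 7.5 | 51% | 62% | 76 |

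A split of 5 against 0 gives Fisher p = 2 × C(50,5)/C(100,5) = 0.056, and 6 against 0 gives 0.027. Even 0 of 50 leaves an exact upper 95% limit of 1 − 0.025^(1/50) = 7.1%.

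The value of 50 per arm comes from Sections 3.C, 3.E, 3.J and 3.P. Section 2 still gives 100 per arm, which would double the event counts.

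**The case against.** A reader might infer that overload is a main expected difference between the arms and that the trial cannot see it. The documents support neither. Section 3.C makes thromboembolism the primary concern. Where Section 1 says which complications are lower with PCC, its examples are lung injury and infection. Section 3.M expects similar adverse event rates. Severe overload could show indirectly through ARDS, dialysis, death or length of stay. The DSMB is to review all data from each arm, and the text never says that its lists are exhaustive.

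Nor is the list built around PCC harms. It includes TRALI, ARDS, hemolytic and allergic reactions, and TRALI and allergy are among the FFP risks that Section 1 names. One item is missing, plus infection, which Section 1 also names.

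The probable direction also limits the damage. Omitting an FFP harm cannot by itself produce a false claim that PCC is as safe as FFP. The safety rate is exploratory, and the added item could not support a formal comparison.

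All of this limits the size of the point and stands to that extent. It does not remove the point. Indirect capture covers only cases that meet another event, and DSMB review does not put overload into the reported rate. An expectation of similar rates is something the trial should examine, so it is no reason to leave out a named harm. Low power is no reason either, since the safety rate is exploratory in any case.

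**Conclusion.** The omission is real and worth correcting, though it does not affect the primary endpoints. Circulatory overload is a risk the protocol attributes to FFP, and neither arm captures it as an event unless it also meets a listed one. The safety comparison in Section 3.P therefore leaves out a named comparator harm.

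FFP probably looks somewhat safer as a result. That direction rests on the protocol's own volume argument and on the assumption that overload is commoner in the FFP arm. The amount cannot be calculated from the documents. The 1, 3 or 5 events per 50 are illustrations at assumed rates, and overload missed in the PCC arm would reduce their effect on the difference. A claim that the trial is clearly tilted against PCC would go beyond this, because the documents give neither overload rates nor a background serious event rate.

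**What to change.** Add circulatory overload to items 5.i and 6.c.iv, with a prespecified standard definition and a seriousness threshold. Collect it identically in both arms and send suspected cases to the existing blinded panel. Report all adjudicated cases by arm, descriptively, with confidence intervals. Count only those that meet the seriousness threshold in the serious adverse event rate, so that milder cases do not blur it. Infection could be considered in the same edit.

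The cost is one line in each list, a case report form field, any supporting data the chosen definition needs, and a few more cases to adjudicate. Some will overlap with TRALI or ARDS, so the plan should say how a case meeting both is counted. Surgical and ICU staff know the product given (Section 3.D), so reporting of suspected cases may differ by arm, and a blinded panel does not fully cure that. For patients already treated, cases would have to be sought in the medical record. No dose, sample size or primary endpoint changes, and the addition gives no useful power for a formal test at 50 per arm.
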